### 10.3 Monitoring for Futility to Assess Vaccine Efficacy

The objective of monitoring the trial for futility to assess VE is to monitor progress toward the minimal needed target number of treatment arm-pooled HIV-1 primary endpoint infections by the end of Stage 1 in the MITT and PP cohorts. Four targets are monitored for:

1. the total number of MITT HIV-1 infections needed to achieve 80% power to detect  $VE(0-24) = 43\%$  (i.e.,  $VE(0-7) = 25\%$ ,  $VE(7-24) = 50\%$  and assuming a constant placebo incidence rate over time),
2. the total number of MITT HIV-1 infections needed to achieve 60% power to detect  $VE(0-24) = 43\%$  (i.e.,  $VE(0-7) = 25\%$ ,  $VE(7-24) = 50\%$  and assuming a constant placebo incidence rate over time),
3. the total number of PP HIV-1 infections needed to achieve 80% power to detect  $VE(7-24) = 50\%$ ,
4. the total number of PP HIV-1 infections needed to achieve 60% power to detect  $VE(7-24) = 50\%$ ,

each calculated based on trial simulations using the R `seqDesign` package. The target numbers in 1.–4. are 108, 65, 79, and 49, respectively. The rationale for considering the four targets is as follows: (i) if the trial cannot achieve 80% power to detect  $VE(7-24) = 50\%$  (targets 1. and 3.), considerations about enrollment modification or expansion are warranted, (ii) if the trial cannot achieve even 60% power to detect  $VE(7-24) = 50\%$  (targets 2. and 4.), considerations about completing the trial early for futility to assess VE are warranted, and (iii) the MITT cohort allows for greater precision of estimation of the number of infections by the end of Stage 1 (targets 1. and 2.), while the PP cohort is used in the primary VE analysis (targets 3. and 4.).

Two versions of the futility monitoring report will be generated. A report provided to the DSMB will be included in 6-monthly closed DSMB reports, starting in October 2018, and will report:

- (a) the estimated distribution of the total (i.e., treatment arm-pooled) number of HIV-1 infections in the MITT cohort by the end of Stage 1, with corresponding power to reject  $H_0 : VE(0-24) \leq 0\%$  using a 1-sided 0.025-level Wald test under the alternative hypothesis that  $VE(0-24) = 43\%$ ,
- (b) the estimated probability that the total number of HIV-1 infections in the MITT cohort by the end of Stage 1 is  $\geq 108$  (target 1) with 95% credible intervals,
- (c) the estimated probability that the total number of HIV-1 infections in the MITT cohort by the end of Stage 1 is  $\geq 65$  (target 2) with 95% credible intervals,

- (d) the estimated distribution of the number of HIV-1 infections in the MITT cohort by the end of Stage 1 in each treatment arm,
- (e) the estimated distribution of the total (i.e., treatment arm-pooled) number of HIV-1 infections in the PP cohort by the end of Stage 1, with corresponding power to reject  $H_0 : VE(7-24) \leq 0\%$  using a 1-sided 0.025-level Wald test under the alternative hypothesis that  $VE(7-24) = 50\%$ ,
- (f) the estimated probability that the total number of HIV-1 infections in the PP cohort by the end of Stage 1 is  $\geq 79$  (target 3) with 95% credible intervals,
- (g) the estimated probability that the total number of HIV-1 infections in the PP cohort by the end of Stage 1 is  $\geq 49$  (target 4) with 95% credible intervals, and
- (h) the estimated distribution of the number of HIV-1 infections in the PP cohort by the end of Stage 1 in each treatment arm.

The distributions in (a), (d), (e), and (h) will also be summarized by the mean number of HIV-1 infections with a Wald 95% confidence interval. The estimation procedures for (a)–(h) will be conducted under each of the following three scenarios:

- (i) the treatment arm-pooled infection rates in (a)–(c) and (e)–(g), and the two treatment arm-specific infection rates in (d) and (h) used for generating future data are based on a Bayesian model and the prior assumptions that  $VE(0-7) = 25\%$ ,  $VE(7-24) = 50\%$  (the design alternative) and the placebo incidence rate is constant over time,
- (ii) the treatment arm-pooled infection rate in (a)–(c) and (e)–(g), and the two treatment arm-specific infection rates in (d) and (h) used for generating future data are based on a Bayesian model and the prior assumption that  $VE = 0\%$  (the null hypothesis), and
- (iii) the treatment arm-pooled infection rate in (a)–(c) and (e)–(g) used for generating future data is based on a Bayesian model and the prior assumption that the infection rate equals the observed to-date infection rate.

The reason for conducting the estimation procedure under (i)–(iii) is that the purpose of the results in (b) is to trigger considerations about enrollment modifications, whereas the purpose of the results in (c) is to trigger considerations about early trial completion due to futility, where it is desired to reach a guideline based on (b) more easily/readily than a guideline based on (c). Accordingly, the results for (b) are interpreted focusing on the prior of  $VE(0-7) = 25\%$  and  $VE(7-24) = 50\%$  (i.e., scenario (i)), which makes it more likely to reach a guideline than the prior of  $VE(0-24) = 0\%$ , and the results for (c) are interpreted focusing on the prior of  $VE(0-24) = 0\%$  (i.e., scenario (ii)), which makes it less likely to reach a guideline than the prior of  $VE(0-7) = 25\%$  and  $VE(7-24) = 50\%$ . Results for (b) and (c) based on carrying forward the observed to-date infection rate in scenario (iii) as well as results for (f) and (g) in scenarios (i)–(iii) based on the PP cohort provide additional

guidance to the DSMB regarding considerations about enrollment modifications or early trial completion.

Furthermore, a treatment-blinded report will be generated for distribution to the OG before each DSMB meeting takes place and will report estimates listed in (a)–(c) and (e)–(g) above calculated based on treatment-blinded data in scenarios (i)–(iii). The reported results pertaining to estimates (a)–(c) and (e)–(g) under scenarios (i)–(iii) will be identical to those in the DSMB report.

In addition, a special DSMB and OG report may be generated approximately 2 months before the projected completion of enrollment in order to provide timely information for a potential decision to modify enrollment before the enrollment apparatus is closed down.

While it is the primary responsibility of the OG to make decisions regarding trial operations and modifications based on the monitoring of treatment-blinded primary endpoints, given the resource issues involved, DSMB review is also needed because issues of scientific integrity are also involved. More specifically, the DSMB can evaluate the progress toward primary endpoint targets in the context of the treatment-unblinded data, and based on this review may recommend to the OG to complete the trial early due to reaching a guideline for futility to assess VE (specified below).

The monitoring for futility to assess VE includes the following guidelines for trial modifications:

- **Guideline for enrollment modifications.** If, in the  $VE(0-24) = 43\%$  scenario for the prior distribution in (i) using the robust prior defined in Section 10.3.2.1, the estimated probability of reaching 108 total infections in the MITT cohort by the end of Stage 1 is less than 25%, the OG may consider enrollment modifications with the intention to be able to conduct the primary VE analysis with sufficiently high power.
- **Guideline for futility.** If, in the  $VE(0-24) = 0\%$  scenario for the prior distribution in (ii) using the standard  $Ga(\alpha, \beta)$  prior as in Section 10.3.2, the estimated probability of reaching 65 total infections in the MITT cohort by the end of Stage 1 is less than 25%, the DSMB may recommend completing the trial early based on the inability to conduct the primary VE analysis with sufficiently high power. However, since this is a proof-of-concept trial, a high bar is desired for completing the trial early for futility, and therefore if this event occurs yet the non-efficacy monitoring has not started or the non-efficacy boundary has not been reached, then this guideline for futility also requires that the estimated  $VE(0-24)$  is  $< 30\%$ .

If enrollment is incomplete at the time of an interim futility analysis, then the outlined estimation procedures will use the average observed enrollment rate in approximately the last 6 months for generating future enrollment data. A Bayesian approach will be used for generating future HIV-1 incidence data, conditional on observed data to-date. More specifically, the estimates in (a)–(c) and (e)–(g) will condition on the observed to-date treatment

arm-pooled HIV-1 incidence rate in the respective cohort, whereas the estimates in (d) and (h) will condition on the observed to-date treatment arm-specific HIV-1 incidence rates in the respective cohorts. All estimates in (a)–(d) and (e)–(g) will also use the observed to-date treatment arm-pooled dropout rate in the respective cohort for generating future dropout data. Further details of these calculations, including the prior distributions, are described in Section 10.3.1.

If, at any time, these guidelines for futility to assess VE are met and yet it appears that value exists in continuing the trial, the statisticians will provide the DSMB and the Leadership Group with additional information, as appropriate, for use in their consideration of whether to recommend early trial completion.

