We consider various different gamma prior distributions for the infection rate in each of scenarios (i)–(iii) reflecting different weights assigned to the prior distribution (see Section 10.3.2 for details). Gamma distributions are considered because they are conjugate to the exponential distribution used for generating future infection data.

At a given interim analysis,  $10^4$  trials are simulated using the above procedure and treatment arm-pooled infection and dropout rates for estimates in (a)–(c) and (e)–(g). Separately, another set of  $10^4$  trials is simulated using the above procedure, treatment arm-specific infection rates, and the treatment arm-pooled dropout rate for estimates in (d) and (h). Each of these trials yields a projected number of infections by the end of Stage 1. These projected numbers of infections from each trial will be used to estimate the entire distribution of the number of infections by the end of Stage 1. The probability of reaching the target number of infections will be estimated as the proportion of trials with the projected number of infections greater than or equal to the target.

Figures on enrollment, HIV-1 incidence and dropout over time will also be included to aid interpretation of the results.

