### 10.3.2 A Bayesian model for the HIV-1 incidence rate in estimation of the number of HIV-1 infection endpoints at an interim analysis

Let  $n_k$  and  $T_k$  denote, respectively, the infection count and the observed total person-time at risk at the time of the  $k$ -th futility analysis, pooling over all treatment arms. Additionally, let  $T^*$  denote the estimated total person-time at risk for the primary efficacy analysis at the end of Stage 1. Let the prior distribution of the pooled HIV-1 incidence rate  $p$  be  $\text{Ga}(\alpha, \beta)$  parametrized such that the prior mean  $E p = \alpha/\beta$  (the same Bayesian method applies to the treatment arm-specific HIV-1 incidence rate). In scenario (i) for the treatment arm-pooled incidence rate, we additionally consider a robust prior distribution described in Section 10.3.2.1 used in the calculation evaluating the enrollment modifications guideline.

Generally, assuming that, conditional on  $p$ , the times to infection follow  $\text{Exp}(p)$ , the posterior mean of  $p$  at the time of the  $k$ -th analysis equals

$$\begin{aligned} E[p \mid \text{data}] &= \frac{\alpha + n_k}{\beta + T_k} \\ &= \frac{\alpha}{\beta} \frac{\beta}{\beta + T_k} + \frac{n_k}{T_k} \frac{T_k}{\beta + T_k}, \end{aligned} \quad (3)$$

i.e., the posterior mean can be interpreted as a convex combination of the prior mean and the observed incidence rate. For a given  $\beta > 0$ , the weight on the prior mean at the first analysis depends on the accumulated person-time at risk ( $T_1$ ), and the weight will decrease in subsequent analyses because  $\beta/(\beta + T_k)$  is a decreasing function of  $T_k$ , which is a desirable Bayesian property.

In order to identify  $\alpha$  and  $\beta$ , it is desirable that the prior mean equals the pre-trial assumed treatment arm-pooled incidence rate  $p^*$  (e.g., under PP VE(7–24)=50%,  $p^* = 0.5 \times 0.042 + 0.5 \times 0.5 \times 0.042 = 0.0315$ ), i.e.,

$$\frac{\alpha}{\beta} = p^*. \quad (4)$$

Furthermore, we propose to consider three values of  $\beta$  that correspond to the weights  $w = \frac{1}{2}$ ,  $\frac{1}{3}$  and  $\frac{1}{4}$  on the prior mean at the time when 50% of the estimated total person-time at risk has been accumulated, i.e., for each value of  $w$ ,  $\beta$  is defined as the solution to the equation

$$\frac{\beta}{\beta + T^*/2} = w.$$

It follows that

$$\beta = \beta(w, T^*) = \frac{wT^*}{2(1-w)}, \quad (5)$$

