and the estimation of  $T^*$  is described in Section 10.3.2.2. For  $w = \frac{1}{2}$ ,  $\frac{1}{3}$  and  $\frac{1}{4}$ , we obtain  $\beta = \frac{T^*}{2}$ ,  $\frac{T^*}{4}$ , and  $\frac{T^*}{6}$ , respectively.

At the  $k$ -th futility analysis and for each of the three values of  $\beta$ , we will sample the treatment arm-pooled HIV-1 incidence rate from the posterior  $\text{Ga}(\alpha + n_k, \beta + T_k)$  for generating future data and report the weight  $\frac{\beta}{\beta + T_k}$  on the prior mean in the convex combination (3).

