### 10.3.2.1 A robust prior model for the HIV-1 incidence rate in the calculation evaluating the guideline for enrollment modifications

The robust prior model (Schmidli et al., 2014) is implemented for the guideline to trigger enrollment modifications since it is designed to maximize the probability of meeting the guideline for large downward deviations from the protocol-assumed incidence rates, while minimizing a false trigger for protocol-assumed incidence rates.

The prior distribution of  $p$  is defined as a weighted mixture of two gamma distributions,

$$(1 - w_R)\text{Ga}(\alpha_I, \beta_I) + w_R\text{Ga}(\alpha_V, \beta_V),$$

where we set  $w_R = 0.2$ , and  $\text{Ga}(\alpha_V, \beta_V)$  and  $\text{Ga}(\alpha_I, \beta_I)$  represent the weakly informative and informative component of the mixture prior, respectively. The parameters  $\beta_V$  and  $\beta_I$  are calculated following (5) with  $w = 1/1000$  and  $w = 1/3$ , respectively (and  $T^*$  per Section 10.3.2.2). Subsequently,  $\alpha_V$  and  $\alpha_I$  are calculated following (4) with  $p^*$  set to the pre-trial assumed treatment arm-pooled MITT incidence rate of 0.0330 infections/person-year at risk for both components of the mixture (i.e., assuming  $\text{VE}(0-7) = 25\%$ ,  $\text{VE}(7-24) = 50\%$ , and a constant placebo incidence rate over time).

The posterior distribution at the time of the  $k$ -th analysis is derived following the conjugacy principle, as in (3), which results in a mixture of conjugate posteriors with updated weights

$$(1 - \tilde{w}_{R,k})\text{Ga}(\alpha_I + n_k, \beta_I + T_k) + \tilde{w}_{R,k}\text{Ga}(\alpha_V + n_k, \beta_V + T_k),$$

where

$$\tilde{w}_{R,k} \propto w_{R,k}f_V / \{w_{R,k}f_V + (1 - w_{R,k})f_I\}$$

with  $f$  equal to

$$f = \frac{\Gamma(\alpha + n_k)/(\beta + T_k)^{\alpha+n_k}}{\Gamma(\alpha)/\beta^\alpha}$$

(see, e.g., Bernardo and Smith, 2000, Section 5.2.3, pages 279–282).

### 10.3.2.2 Estimation of the total person-years at risk by the end of Stage 1

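### Futility scenario (iii) uses the observed infections twice, so its projected infection totals are spread too narrowly, mainly at early analyses

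*SAP*

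**What the plan says.** SAP 10.3 projects the pooled number of infections by the end of Stage 1 against four targets: 108 and 65 (MITT), 79 and 49 (per-protocol). Each report gives the estimated distribution of the total and the probability of reaching each target, with 95% credible intervals, under three scenarios. Scenarios (i) and (ii) take their prior from the design alternative and from the null. Scenario (iii) takes it from "the prior assumption that the infection rate equals the observed to-date infection rate".

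Four further statements fix how scenario (iii) works:

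- SAP 10.3: "A Bayesian approach will be used for generating future HIV-1 incidence data, conditional on observed data to-date".
- SAP 10.3.1: "We consider various different gamma prior distributions for the infection rate in each of scenarios (i)–(iii) reflecting different weights assigned to the prior distribution".
- SAP 10.3.2: β is chosen to give weight w = 1/2, 1/3 or 1/4 "on the prior mean at the time when 50% of the estimated total person-time at risk has been accumulated". This gives β = T*/2, T*/4 or T*/6.
- SAP 10.3.2: "we will sample the treatment arm-pooled HIV-1 incidence rate from the posterior" Ga(α + n_k, β + T_k), where n_k is the infection count and T_k the person-time observed so far.

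SAP 10.3 describes the scenario (iii) results as extra guidance for the DSMB on changing enrolment or finishing early. The Oversight Group receives the same pooled results.

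**The concern.** In scenarios (i) and (ii) the prior comes from pre-trial assumptions, so giving it a weight means something: it is information from outside the data. In scenario (iii) the prior mean is the observed rate itself. Giving that prior 761 to 2,283 person-years of weight and then adding the observed person-time counts the same infections again. The posterior stays centred on the observed rate but claims far more person-time than the trial has accrued.

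Scenario (iii) is the view meant to show what the accruing data imply by themselves. SAP 10.3.1 justifies the Bayesian approach as a way to stabilise the rate when infections are few. A prior centred on the observed rate cannot do that: a rate that is low by chance is kept, and false precision is added. The overstatement is largest when data are sparsest.

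**Working it through.** **Inputs.** N = 2600, 2 years of follow-up, dropout d* = 0.10 per person-year (SAP 10.3.2.2), and the "pre-trial assumed treatment arm-pooled MITT incidence rate of 0.0330 infections/person-year at risk" (SAP 10.3.2.1). The values of w, β and the posterior are from SAP 10.3.2. SAP 10.3.2.2 itself uses 0.2T* and 0.3T* as examples of the first analysis.

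**Reproducing the SAP's figures.** T* = N(1 − exp(−2(p* + d*)))/(p* + d*) = 2600 × (1 − exp(−0.266))/0.133 = 4565.85, as stated. The prior weight is β/(β + T_k). At 0.2T* it is 0.714, 0.556 and 0.455 for w = 1/2, 1/3 and 1/4. At 0.3T* it is 0.625, 0.455 and 0.357. Both sets agree with the SAP to its rounding.

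**Posterior in scenario (iii).** Setting α/β = n_k/T_k gives α = β·n_k/T_k. The posterior is then Ga((n_k/T_k)(β + T_k), β + T_k):

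- mean n_k/T_k, unchanged;
- variance (n_k/T_k)/(β + T_k), against (n_k/T_k)/T_k when the data are used once;
- SD ratio for the rate √(T_k/(T_k + β)), which does not depend on n_k.

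At T_k = 0.2T* = 913.17 and w = 1/2, β = 2282.93, so 913 observed person-years are treated as 3,196.

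**Infection total.** With R = T* − T_k person-years to come, the future count is negative binomial with mean μ = R·n_k/T_k and variance μ(1 + R/(β + T_k)). Setting β = 0 gives the data-once variance. At 0.2T* and w = 1/2, the two factors are 1 + 0.8/0.7 = 2.143 and 1 + 0.8/0.2 = 5, so the SD ratio is √(2.143/5) = 0.65.

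| T_k | Rate SD ratio (w = 1/2, 1/3, 1/4) | Predictive SD ratio for the total | Coverage of nominal 95% predictive interval |
|---|---|---|---|
| 0.2T* | 0.53, 0.67, 0.74 | 0.65, 0.75, 0.80 | 80.4%, 85.9%, 88.5% |
| 0.3T* | 0.61, 0.74, 0.80 | 0.75, 0.83, 0.87 | 86.7%, 89.8%, 91.6% |
| 0.5T* | 0.71, 0.82, 0.87 | 0.87, 0.91, 0.94 | 91.7%, 93.2%, 93.8% |

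Coverage comes from 200,000 simulated trials at a true rate of 0.033. Using the data once gives 95.0%, 95.2% and 95.4% in the three rows.

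**Examples with whole counts at 0.2T*.** For n_k = 19 (observed rate 19/913.17 = 0.0208), the projected mean is 95 in every row:

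| Posterior | Predictive SD | 95% range of total | P(total ≥ 108) |
|---|---|---|---|
| Data once, Ga(19, 913.17) | 19.5 | 61–137 | 0.246 |
| w = 1/1000, centred on n_k/T_k | 19.5 | 61–137 | 0.245 |
| As written, w = 1/4 | 15.6 | 67–128 | 0.204 |
| As written, w = 1/3 | 14.5 | 69–126 | 0.190 |
| As written, w = 1/2 | 12.8 | 72–122 | 0.163 |

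The error pushes a target probability away from one half, in either direction. For n_k = 15, P(total ≥ 65) is 0.710 with the data used once, against 0.769, 0.787 and 0.822 as written (w = 1/4, 1/3, 1/2).

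**The case against.** **The text is not fully explicit.** No α or β is written out for scenario (iii). Equation (4) ties the prior mean to the pre-trial rate, and SAP 10.3.1 also describes the prior as pre-trial. The double use is therefore inferred from several sections read together. That is fair, but the other readings do not help. A pre-trial prior mean contradicts the definition of scenario (iii). A fixed plug-in rate contradicts the statement that weighted priors apply in all three scenarios, and it would be narrower still: for n_k = 19 the SD would be √76 = 8.7 against 19.5.

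**The projection is unbiased and the problem fades.** Both are true. At 0.5T* the predictive SD is only 6% to 13% too small. Reports run every six months, so the early ones carry most of the error.

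**A reader might infer that the narrowing could push the trial across a 25% guideline.** The documents do not support this. SAP 10.3 ties the enrolment guideline to scenario (i) with the robust prior and the futility guideline to scenario (ii). Neither uses scenario (iii) or the per-protocol targets. Even with 25% as an informal benchmark for 108 infections, whole counts at 0.2T* do not change side: n_k = 19 gives 0.246 against 0.163–0.204, all below, and n_k = 20 gives 0.330 against 0.274–0.304, all above. At 0.3T* one case does, and only just: n_k = 30 with w = 1/2 (0.295 against 0.249).

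**The change comes late.** The current SAP is dated July 18, 2022, after the May 28, 2021 target data cut for the end of Stage 1. A correction now would not alter reports already issued. It still bears on how they are read and on any reuse of the method, and the date does not make the method right.

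**Conclusion.** The point holds. As written, scenario (iii) uses the data twice and reports too little uncertainty. The predictive SD of the infection total is 20% to 35% too small at 0.2T*, 13% to 25% at 0.3T* and 6% to 13% at 0.5T*. The mean projection is right. The consequence is overconfident supplementary guidance to the DSMB and the Oversight Group, mainly at early analyses. It is not an error in either formal guideline.

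The figures assume remaining person-time of T* − T_k with T* = 4565.85, and they ignore uncertainty in enrolment and dropout. The infection counts are illustrative. The SD ratios depend only on T_k/T* and w, but the coverage figures assume a true pooled rate of 0.033.

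**What to change.** State in SAP 10.3 and 10.3.2 that scenario (iii) uses the observed data once. Either draw the rate from Ga(n_k, T_k), or use the weakly informative component already specified in SAP 10.3.2.1 (w = 1/1000), centred on n_k/T_k. The second option has β = T*/(2 × 999) = 2.3 person-years, which is negligible beside 913, and it reproduces the data-once results above. Remove scenario (iii) from the SAP 10.3.1 sentence on differing prior weights. Leave scenarios (i) and (ii) and both guidelines unchanged.

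The cost is a sentence or two of SAP text, a small change to the simulation code, and wider reported intervals for scenario (iii). For reports already issued, a note that the scenario (iii) spread was understated would be enough.
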